7.2 Primary Outcome

The primary outcome is average daily hours of hearing aid use at one year, as measured through objective hearing aid data logging. If a participant wears a hearing aid in both ears, then the ear with the greatest number of hours logged will be selected.

7.3 Primary Analysis

We will use a weighted regression model with an identity link to compare average daily hours of hearing aid use at one-year post-randomization between participants assigned to the telehealth HHC or conventional HHC. To account for the non-normal distribution of the outcome, confidence intervals and p-values will be obtained using a bias corrected and accelerated bootstrap resampling procedure with 10,000 replicates. Consistent with best practices in clinical trials, we will assess the comparability of the randomized groups with respect to potential confounders [13], such as recruitment source, site, level of hearing impairment, Quick Speech in Noise score, self-reported acceptance of telehealth at baseline, self-reported and objectively measured baseline hours of hearing aid use, self-reported baseline hours of hearing assistive technologies use, the number of days hearing log data was measured prior to randomization, and the number of visits prior to randomization at which a participant provided hearing logging data. If there is an imbalance between randomized treatment assignment we may adjust for relevant confounders as well as explore the use of a prespecified inverse probability of treatment weight [14] or a precise, locally efficient, augmented, simple estimator [15]. A logistic regression model will be used to model the probability of attrition according to the confounders described above plus age, sex, and applicable interactions. Inverse probability of attrition weights will be calculated and either included in the model for the primary outcome directly or cross-multiplied with inverse probability of treatment weights.

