7.9 Characterization of participants who leave the study early

A final interview will be attempted with all participants who are either unable (e.g., due to illness) or unwilling to complete the study. Trained interviewers will collect information by telephone or HIPAA-compliant video call regarding the reason for withdrawal and offer to schedule a home visit/telephone/video call for an abbreviated final study session. In the absence such a session, because dropouts may be more likely to have dementia, we will attempt to ascertain dementia status using a telephone-based/video call-based assessment with the participant or informant interview conducted with a knowledgeable informant.

In the case where the participant is alive and able to communicate by phone/video call, we will administer the Six Item Screener (SIS). The SIS is a short instrument developed to identify cognitive impairment in older adults. In the case where the participant has died or is otherwise unable to communicate by phone/video call, dementia status will be characterized by informant interview via telephone/video call using the AD8--a brief instrument, derived from the Clinical Dementia Rating Scale, developed to discriminate between normal aging and dementia. Notably, these procedures parallel ARIC's ongoing dementia surveillance methods. For ARIC participants, additional sources of information may also be used to complete ascertainment of dementia cases (e.g., discharge codes from hospitalizations, CMS, and ICD codes on death certificates).

8 Randomization

Participants will be randomized in a 1:1 ratio to the telehealth HHC vs. conventional HHC delivery groups. Randomization will be carried out using random blocks of sizes 2, 4, and 8, and will be stratified by degree of hearing loss (mild vs. moderate or greater), cohort (originally recruited from the ARIC Study or de novo from the community), and field center to achieve balance among these factors between HHC arms.

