11.2 Analytic approach

The final statistical analysis plan was finalized in discussions between the study investigators and coordinating center.

The comparison for all primary analyses is randomization to the telehealth HHC vs. conventional clinic-based HHC delivery model under the intention-to-treat paradigm, analyzing individuals according to their random allocation, irrespective of the treatment received.

Consistent with best practices in clinical trials, we will assess the comparability of the randomized groups with respect to known confounders, such as recruitment source, site, level of hearing impairment, Quick Speech in Noise score, self-reported acceptance of telehealth at baseline, self-reported and objectively measured baseline hours of hearing aid use, self-reported baseline hours of hearing assistive technologies use, the number of days hearing log data was measured prior to randomization, and the number of visits prior to randomization at which a participant provided hearing logging data.⁴⁸ These variables will be considered as covariates in all models. If there is an imbalance between randomized treatment assignment, we may adjust for relevant confounders as well as explore the use of a prespecified inverse probability of treatment weight or a precise, locally efficient, augmented, simple estimator.^{49,50} A logistic regression model will be used to model the probability of attrition according to the confounders described above plus age, sex, and applicable interactions. Inverse probability of attrition weights will be calculated and either included in the model for the primary outcome directly or cross-multiplied with inverse probability of treatment weights.

We will use a weighted regression model with an identity link to compare average daily hours of hearing aid use at 1-year post-randomization between participants assigned to the telehealth HHC or conventional HHC. To account for the non-normal distribution of the outcome, confidence intervals and p-values will be obtained using the bias corrected and accelerated bootstrap resampling procedure with 10,000 replicates.

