7.4 Sensitivity Analyses of the Primary Outcome

Additional analyses of the primary outcome may include, but are not limited to:

1. A replication of the primary analysis with stratification by recruitment source (ARIC vs de novo). An interaction between treatment assignment and recruitment source will be tested relative to $p < 0.10$.
2. An analysis of subjective, self-reported hours of hearing aid use including differences between the use of hearing aids and hearing assistive technologies.
3. An analysis restricted to participants who wore the same type of hearing aid.
4. Exploration of the impact on the primary analysis by further adjustment for additional explanatory variables.

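### The primary regression commits no covariates: adjustment for baseline logged hours and the stratification factors is optional and depends on an undefined imbalance

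*SAP*

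**What the plan says.** The model statement in SAP 7.3 reads "We will use a weighted regression model with an identity link to compare average daily hours of hearing aid use" between arms at one year, with bias-corrected and accelerated bootstrap inference. It names no covariate. An open list of potential confounders follows. It includes objectively logged baseline hours, recruitment source, site and level of hearing impairment, but its stated purpose is to check that the arms are comparable. Then comes "If there is an imbalance between randomized treatment assignment we may adjust for relevant confounders", and the team may also "explore the use of a prespecified inverse probability of treatment weight" or an augmented estimator. The SAP gives no metric or threshold for imbalance, and neither document writes out the treatment-weight model.

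The attrition weights are firmer. They will be calculated from a logistic model on the listed variables plus age, sex and applicable interactions, and are then "either included in the model for the primary outcome directly or cross-multiplied with inverse probability of treatment weights".

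SAP 7.4, item 4, offers "Exploration of the impact on the primary analysis by further adjustment for additional explanatory variables", which presupposes a primary adjustment set that 7.3 does not fix.

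Protocol 2.1 and 11.2 carry a sentence that the SAP lacks: "These variables will be considered as covariates in all models". In 11.2 the next sentence is again conditional: "If there is an imbalance between randomized treatment assignment, we may adjust for relevant confounders". Under Protocol 8, randomization "will be stratified by degree of hearing loss (mild vs. moderate or greater), cohort" and field center. Spouse or partner pairs have their own strata, defined by pair-level ARIC status and field site, without hearing loss.

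**The concern.** The two documents together do not tell a programmer whether the primary model is adjusted or for what. The SAP text points to an unadjusted model with optional repair. The protocol can be read as adjustment throughout.

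The trigger itself also works poorly. Factors used in stratified block randomization are balanced by design, so a balance check would rarely select them. Leaving them out still gives intervals that are too wide if they are prognostic. Baseline logged hours are the same measurement as the outcome, so adjusting for them should reduce residual variance whether or not the arms differ at baseline. The cohort is fixed by the parent trial, so lost precision cannot be recovered by enrolling more people.

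SAP 7.1 says the plan predates review of the dataset and that unblinding follows database lock. SAP 7.1 and 8 archive specifications and changes. This leaves an audit trail, but nothing requires the covariate and weight choice to be made before treatment labels are available.

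**Working it through.** **1. The plan's own figure.** Inputs from SAP 5: 340 randomized, 5% lost per year, 322 analyzed, 80% power, 5% type I error, detectable difference 1.5 h. Sidedness is not stated; two-sided is assumed, with equal arms.
- Retention: 340 × 0.95 = 323, against 322 stated. This agrees to within one participant.
- The 1.5 h cannot be reproduced because no SD is given. Solving backwards: SD = 1.5 / [(1.96 + 0.8416) × √(4/322)] = 1.5 / 0.3123 = 4.80 h.

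**2. Adding baseline logged hours.** If 1.5 h is an unadjusted figure (the SAP does not say), the adjusted detectable difference is 1.5 × √(1 − r²), where r is the correlation between baseline and 1-year hours. The equivalent gain in sample size is 1/(1 − r²). The documents do not give r, so a range is assumed.

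| Assumed r | Detectable difference (h) | Power for 1.5 h | Sample equivalent |
|---|---|---|---|
| 0 (unadjusted) | 1.50 | 80% | 1.0 |
| 0.3 | 1.43 | 83.6% | 1.1 |
| 0.5 | 1.30 | 89.9% | 1.3 |
| 0.7 | 1.07 | 97.5% | 2.0 |
| 0.8 | 0.90 | 99.7% | 2.8 |

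**3. The same with the protocol's implied SD.** Protocol 11.1 gives 0.8 to 0.9 h with 10–20% loss from 400, so N = 360 to 320.
- 0.8 / (2.8016 × √(4/360)) = 2.71 h; 0.9 / (2.8016 × √(4/320)) = 2.87 h.
- At N = 322 these SDs give 0.85–0.90 h unadjusted, and 0.81–0.86, 0.73–0.78, 0.60–0.64 or 0.51–0.54 h for r = 0.3, 0.5, 0.7 or 0.8. The proportional gain does not depend on the SD.

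**4. Leaving out the stratification factors.** If they explain a share R² of outcome variance and are balanced by design, the unadjusted test has actual size 2 × [1 − Φ(1.96/√(1 − R²))]. For an assumed R² of 5%, 10% or 20% this is 4.4%, 3.9% or 2.8% instead of 5%. A simulation of stratified blocks (N = 322, 16 strata, R² = 10%, no baseline effect, normal outcome, ordinary least squares, 4,000 null runs) gave 4.1% unadjusted and 5.2% adjusted, with Monte Carlo error of 0.3–0.4 points.

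**5. A mechanical imbalance trigger.** The SAP gives no threshold, so baseline p < 0.10 is used for illustration. With 40,000 null trials, 161 per arm, one covariate and least squares, adjusting only when triggered gave a size of 3.9%, 3.0% or 2.3% for r = 0.5, 0.7 or 0.8. Always adjusting gave 4.8–5.0%.

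**6. Cost of the covariates.** Baseline hours 1 + hearing loss 1 + cohort 1 + field center 3 = 6 parameters. The detectable difference grows by √(320/314) = 1.0095, about 1%. This is repaid once the covariates explain 1 − 314/320 = 1.9% of variance.

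**7. Missing baseline logs.** The share is not given; 10% missing at random is assumed.
- Dropping those participants: 1.5 × √((1 − r²)/0.9) = 1.51 h at r = 0.3, slightly worse than unadjusted, and 1.37 h at r = 0.5.
- Mean imputation plus a missing indicator: 1.5 × √(1 − 0.9r²) = 1.44 h and 1.32 h.

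**The case against.** The protocol's covariate sentence can be read as a commitment to treat the listed variables as covariates, and the synopsis carries no imbalance trigger. On that reading the fault is only a disagreement between protocol and SAP, and a short covariate list would cut the protocol's longer one. The ambiguity is real. It is a reason to reconcile the documents and to keep the remaining variables in a sensitivity analysis. It does not show that the primary model is fixed, because Protocol 11.2 goes straight on to optional adjustment and the SAP drops the sentence.

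A reader might infer that the weighting is wholly unspecified. It is not: attrition weights are committed with a largely named model. The choice between direct use and cross-multiplication most naturally depends on whether a treatment weight is used. That treatment weight, the augmented estimator and the interactions in the attrition model are what remain open.

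A reader might also infer inflated type I error. Choosing the smaller of the adjusted and unadjusted p-values would give 7.2–8.5% in the setting of step 5, but neither document proposes such a choice. The errors shown for a mechanical trigger, or for omitting the strata, are conservative.

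Finally, the sizes are conditional, and the simulations use normal outcomes and least squares without the planned bootstrap or attrition weights. That limits confidence in the magnitude, not in the direction.

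**Conclusion.** The point holds. The SAP commits no covariate to the primary model, makes adjustment optional on an undefined imbalance, and differs from the protocol on whether the listed variables enter the models. Always adjusting for a few variables that are already collected is a better rule than a trigger.

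The likely gain runs from about 5% off the detectable difference at r = 0.3 to 40% at r = 0.8. It rests on an assumed correlation, a back-solved SD and the assumption that the stated differences are unadjusted. The loss from omitting the stratification factors depends on an assumed share of variance.

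This does not show that a stated sample-size figure is wrong. It should be corrected before unblinding, but it does not undermine the randomized comparison.

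**What to change.** In SAP 7.3, with matching text in Protocol 2.1 and 11.2, before unblinding:

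> The primary weighted regression always includes arm, objectively logged baseline hours, hearing-loss level, recruitment cohort and field center, regardless of observed balance. Weights are the inverse probability of attrition weights only. Treatment weighting, the augmented estimator and adjustment for the remaining listed variables are sensitivity analyses.

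Also state:
- **Which log is baseline.** Protocol 7 and SAP 4 make the Year 3 visit the baseline. Protocol 9.1 and Table 1 also place a check-up at the randomization visit, before participants learn their arm, and Protocol 7.2.1 includes data logging at in-person check-ups. SAP 4 allows up to 9 months between Year 3 and randomization, and longer for some at one site. Choose one log in advance and use the other when the first is missing.
- **Missing baseline.** Give a rule that drops no randomized participant, such as mean imputation plus a missing indicator.
- **Attrition model.** List its interactions.
- **Pairs.** Say how spouse or partner pairs are coded for the strata, since theirs differ (Protocol 8).
- **HHIE-S.** If it is analyzed as continuous, include its own baseline value, which Table 1 collects. This does not carry over to the single 5-point IOI-CHI item, because SAP 7.5 applies the primary approach only to continuous outcomes.

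The work is wording and a little programming. The statistical price is that in step 6, and no new data are needed.

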7.2 Hearing intervention assessment

7.2.1 Intervention Check-Up

The ACHIEVE-HIFU Intervention Check-Up includes assessments of the following components related to the hearing intervention at the in-person semi-annual and annual visits, and some of the components, as noted below, during both scheduled and unscheduled remote encounters.

- **Hearing aids:** usage of all hearing aids is documented [all contacts]
- Real-ear aided response: real-ear measure to verify the gain and output of hearing aids [in-person visits only; as needed]
- **Speech intelligibility index**: a calculated estimate from the real-ear measurements that indicates the amount of the speech signal available to the participants when wearing their hearing aids [in-person visits only; as needed]
- **Hearing aid data logging:** hearing aid use is obtained from the device data log within the hearing aid manufacturer software, including the total hours of use and average hours of use per day [in-person visits only]
- Hearing assistive technologies (HAT): usage of HATs is documented [all contacts]
- Quick speech in noise (QuickSIN; aided): assesses speech recognition in noise
 utilizing the hearing aids, where sentences are presented in the presence of background
 noise, and the participant repeats back what they heard [in-person annual visits only]

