11.1 Sample size

This study is predicated on an already established cohort with a fixed sample size from the original ACHIEVE trial (N=490 for the clinic-based hearing intervention cohort). In order to estimate the minimal difference in hours of continued hearing aid use that could be detected between the telehealth and conventional HHC groups after 12 months, we've made conservative assumptions based on expected loss to follow-up over time that would diminish the sample size and any observable outcomes. The initial cohort receiving the hearing intervention was N=490. Assuming conservatively that 5% of participants per year in this cohort are lost to follow-up or death, we would have a potential cohort of N=420 participants who would be eligible to participate after 3 years of follow-up from 2021-2022. If we further assume that up to 5% of these participants may then decline additional follow-up, we conservatively estimate that N=400 participants currently in the hearing intervention group will be recruited into this follow-up study (ACHIEVE-HIFU). Further conservatively assuming: 1) 10-20% loss to follow-up in the 12-month follow-up data collection; 2) 80% power and a 5% Type 1 error rate; and 3) that patterns of hearing aid utilization will be similar to those observed in the ACHIEVE pilot study, we would have the ability to detect an average treatment effect of 0.8 to 0.9 hours of hearing aid use between the telehealth HHC and conventional HHC arms.

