ACHIEVE-HIFU is predicated on a finite sample of participants recruited from the treatment arm of the parent ACHIEVE study. An estimated 340 participants will be randomized to telehealth HHC or conventional HHC. Assuming conservatively that 5% of participants are lost to follow-up or death each year, we would have a sample of N=322 participants one-year post-randomization. With 80% power and a 5% Type 1 error rate, this sample would have the ability to detect an average treatment effect of 1.5 hours of hearing aid use between the telehealth HHC and conventional HHC arms.

6. Analysis Populations

Analyses will follow the intention-to-treat (ITT) principle in which participants will be analyzed in the condition to which they were randomized, regardless of whether they received the assigned intervention. Primary analyses will be based on the ITT population, which includes all randomized participants.

7. Statistical Analysis

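### SAP 7.3 leaves adjustment for logged baseline hours optional, and its attrition model is not assured to correct loss that relates to hearing aid use differently by arm

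*SAP*

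**What the plan says.** **Population.** SAP section 6: "Primary analyses will be based on the ITT population, which includes all randomized participants".

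**Covariates.** SAP 7.3 gives an open-ended list of baseline variables to compare between arms, including objectively measured baseline hours. If there is imbalance, "we may adjust for relevant confounders as well as explore the use of a prespecified inverse probability of treatment weight", or an augmented estimator. Protocol 2.1 (Synopsis) and 11.2 give the same list and add: "These variables will be considered as covariates in all models". The SAP does not repeat that sentence.

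**Missing Year 1 hours.** SAP 7.3 and Protocol 11.2 share the remedy. A "logistic regression model will be used to model the probability of attrition according to the confounders described above plus age, sex, and applicable interactions", and the resulting weights enter the outcome model, alone or multiplied by treatment weights. Logged baseline hours are therefore in the attrition model. Arm and 6-month hours are not named, and the interactions are left open.

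**When logs are read.** Protocol 7.2.1 describes check-up components "related to the hearing intervention at the in-person semi-annual and annual visits". The device log gives use "including the total hours of use and average hours of use per day [in-person visits only". Table 1 schedules the check-up at 6 months, and both arms are seen in clinic every 6 months (Protocol 9.1, 9.3).

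**Expected loss.** SAP section 5 assumes 5% a year: "we would have a sample of N=322 participants one-year post-randomization", with a detectable effect of 1.5 h. Protocol 11.1 assumes 400 recruited, "10-20% loss to follow-up in the 12-month follow-up data collection", and 0.8 to 0.9 h.

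**Sensitivity analyses.** SAP 7.4 lists four optional analyses. None deals with missing Year 1 hours.

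**The concern.** There are two linked issues.

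The first is precision and needs no story about dropout. Hours logged before randomization should predict hours logged a year later. Such a covariate narrows the interval whether or not the arms are balanced on it, so imbalance is the wrong trigger. The cohort is fixed, so precision cannot be bought with more participants.

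The second is attrition. A model without arm gives the same weight to the same baseline profile in both arms. If low users are lost mainly from one arm, such weights leave the difference among completers where it was. The documents make this possible without showing that it happens. The trial is unmasked, one arm has extra remote contact, and logs are read only in person. A home visit counts as face-to-face in Protocol section 3, so a log may be read there. A telephone or video session (Protocol 5.2, 7.9) yields none.

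**Working it through.** **1. Planning figures.** 340 x 0.95 = 323, against the stated 322. Protocol: 490 x 0.95^3 = 420, and 420 x 0.95 = 399, stated as 400. Losses of 10% and 20% leave 360 and 320.

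**2. Implied SD.** Neither document states an SD. For an unadjusted 1:1 comparison with 80% power and two-sided 5% (sidedness assumed), SD = effect / (2.80 x sqrt(4/N)):
- SAP: 1.5 h at N = 322 gives 4.80 h.
- Protocol: 0.8 h at N = 360 gives 2.71 h, and 0.9 h at N = 320 gives 2.87 h.

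**3. Precision.** A covariate with correlation r to the outcome multiplies the SE by sqrt(1 - r^2). The correlation is assumed.
- r = 0.50: 1.5 x 0.866 = 1.30 h
- r = 0.67: 1.5 x 0.742 = 1.11 h
- r = 0.80: 1.5 x 0.600 = 0.90 h

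In simulation at r = 0.67, the SE fell from 0.53 to 0.40 h.

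**4. Bias from differential loss.** Assumptions, none from the documents: true effect 0; normal hours; equal loss in both arms; correlations baseline-6m / 6m-12m / baseline-12m of 0.75 / 0.82 / 0.67. Log-odds of loss are 0.9 per SD lower 6-month use in the conventional arm and 0 in the telehealth arm. The weights use the listed terms without arm. Bias is telehealth minus conventional; reversing the arms reverses the sign.

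| Set | Listed weights only | With baseline-hours covariate | Covariate and added terms |
|---|---|---|---|
| SAP: N=340, 5% loss, SD 4.80 | -0.17 h | -0.07 h | 0.00 h |
| Protocol: N=400, 10% loss, SD 2.71 | -0.19 h | -0.07 h | 0.00 h |
| Protocol: N=400, 20% loss, SD 2.87 | -0.39 h | -0.15 h | 0.00 h |

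The added terms are arm, 6-month hours, arm x baseline hours and arm x 6-month hours. The zeros in the last column are expected, because that model contains the variable that drives loss in the simulation.

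Against the detectable effects, the first column is 0.17/1.5 = 11%, 0.19/0.8 = 24% and 0.39/0.9 = 43%. The second is 0.07/1.5 = 5%, 0.07/0.8 = 9% and 0.15/0.9 = 17%.

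**5. How far this depends on the assumptions.**
- Equal slopes in both arms: about 0 h.
- Milder contrast (0.9 against 0.45): SAP -0.08 h, or -0.03 h with the covariate. Protocol -0.09 and -0.19 h, or -0.03 and -0.07 h.
- Correlations 0.60/0.70/0.50: SAP -0.15 and -0.08 h. Correlations 0.85/0.90/0.80: SAP -0.19 and -0.05 h.
- The other SAP 7.3 options, SAP set: treatment weights leave -0.17 h; the augmented estimator leaves -0.07 h.
- Arm and arm x baseline hours only, with the covariate: still -0.07 h (SAP set).

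**6. What drives loss decides what helps.**
- Baseline use: the covariate alone leaves 0.00 h in all three sets, and the 6-month terms add nothing.
- 6-month use: as in the table.
- 12-month use: the covariate alone leaves -0.11, -0.13 and -0.27 h; the added terms still leave -0.07, -0.08 and -0.16 h.

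**The case against.** The strongest reply is that the plan already has room for everything asked. The variable list is open-ended, the unspecified interactions could include arm, SAP 7.4 item 4 allows further adjustment, and SAP 7.1 foresees changes when data are missing. The Protocol sentence on covariates, given twice, can be read as a commitment, with the optional wording reserved for extra imbalance. On that reading no precision is lost, and the residual bias in the SAP set is -0.07 h. This stands as far as it goes: the plan permits the right terms. But it fixes none, the SAP drops the Protocol sentence, and choosing missing-data terms after seeing the data is what prespecification should prevent.

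A second reply is that differential loss is assumed. That also stands. An odds ratio of about 2.5 per SD in one arm and none in the other is a strong contrast. Even then, the SAP-set bias is 0.17/0.53, about a third of an SE. The larger shares use the Protocol's planning figures, and neither document reports actual loss.

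A reader might go further and infer that differential loss will go uncorrected, or that 6-month hours are needed to correct it. The documents support neither. The interactions may include arm, no loss pattern is reported, and the value of 6-month hours depends on what drives loss.

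**Conclusion.** The point holds in two parts of unequal weight.

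The firmer part is the covariate. The SAP makes adjustment for logged baseline hours optional and tied to imbalance, and the Protocol reads differently. The gain from fixing it is a detectable effect of about 1.1 h instead of 1.5 h (1.3 to 0.9 h over correlations 0.50 to 0.80). This holds if 1.5 h was an unadjusted figure; SAP section 5 states neither the SD nor the model.

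The weaker part is attrition. Correction of loss that relates to use differently by arm is not assured. Under the assumed strong contrast the bias is small at the SAP's 5% loss and a larger share of the target at the Protocol's 10-20%. The covariate removes roughly 60% of it when 6-month use drives loss (43-76% over the correlations tested). The extra attrition terms are a cheap improvement, not a demonstrated need. All bias figures rest on assumed correlations, slopes and normal hours, although SAP 7.3 describes the outcome as non-normal.

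**What to change.** 1. **Main change.** Make objectively logged baseline hours a fixed covariate in the primary outcome model, whether or not the arms are imbalanced. Align SAP 7.3 with Protocol 2.1 and 11.2.

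2. **Secondary change.** State which interactions enter the attrition model. Add arm, arm x baseline hours, 6-month logged hours and arm x 6-month hours, keeping the listed variables, age and sex. The 6-month hours enter only the weights, so the treatment effect is not conditioned on them. Give a fallback when the 6-month log is missing, for example baseline hours. With 50% of dropouts and 10% of completers lacking that log, the remaining bias was -0.02 h (SAP), -0.02 h (Protocol 10%) and -0.04 h (Protocol 20%) when 6-month use drives loss. Re-estimate the weights in each bootstrap sample and state how near-separated refits are handled.

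3. **Sensitivity analysis.** Add one delta-adjusted analysis for missing Year 1 logs to SAP 7.4, because the added terms cannot fully correct loss driven by later, unseen use. For scale, a 1-SD shift among those missing in one arm moves the difference by loss share x SD: 0.05 x 4.80 = 0.24 h, 0.10 x 2.71 = 0.27 h, 0.20 x 2.87 = 0.57 h.

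**Cost.** SAP wording and modest programming; the data are already scheduled. The added terms did not raise the simulated SE with the covariate in the model (0.40 and 0.40 h in the SAP set; 0.22 and 0.21 h, and 0.25 and 0.24 h, in the Protocol sets). The real difficulty is sparse events: 340 x 0.05 = 17 dropouts for 18 terms in the model as simulated. Near-separated refits at 5% loss depended on how the listed terms were coded. One check found 27-31% with or without the added terms; another found a rise from 2% to 13% when they were added.
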